- Within-host variation in influenza strains between the first and the third viral swab
- Cost effectiveness, assessed using health resource utilization (visit to clinic, hospital, pharmacy, emergency department) and school and work absenteeism
- Proportion with antiviral resistance, assessed by genetic sequencing of influenza strains from the drug eligible and drug ineligible study participants

Hypothesis

Primary hypothesis:

- A home-based approach to influenza infection control will result in a large percentage of drug eligible individuals diagnosed with influenza initiating antiviral therapy within 48 hours of symptom onset.

Secondary hypotheses:

- Home-based approach to influenza infection control and rapid delivery of antiviral therapy will decrease symptom severity in the drug eligible individuals diagnosed with influenza that administer antiviral therapy within 48 hours of symptom onset compared to drug eligible, influenza-infected individuals that administer antiviral therapy greater than 48 hours after symptom onset.
- Home-based approach to influenza infection control and rapid delivery of antiviral therapy will decrease the duration of viral RNA detection in the drug eligible, influenza-infected individuals that administer antiviral therapy within 48 hours of symptom onset compared to drug eligible, influenza-infected individuals that administer antiviral therapy greater than 48 hours after symptom onset.

IV. Study Population

The study will be conducted in households with at least 3 members, where at least 2 of these members must be eligible to receive BXM, in the Seattle area. Participants aged 12 years or older, weighing at least 40 kg, will be drug eligible. Participants of any age that reside in the same household as the case at least 4 days per calendar week will be drug ineligible study participants. Drug eligible study participants will receive baloxavir intervention when appropriate,

and all drug eligible and drug ineligible participants will receive a 7-day follow-up from the study team per illness episode.

Study size

The study is being conducted in the Seattle, WA area over one influenza season. The goal is to enroll 250 households, with enrollment occurring prior to and during the annual influenza season.

Household enrollment criteria

The household must meet all the following enrollment criteria:

Household inclusion criteria

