4. Additionally, one week later, the ill individual will complete day 7 of the illness questionnaire, which will ask information about respiratory and systemic symptoms, recent travel history, and absenteeism in 7 calendar days following the onset of a cough in the ill participant.

Immediately following the onset of an acute cough or 2 or more respiratory symptoms in a drug eligible participant, the following procedures will occur:

1. The person will self-test for influenza using the prepositioned home-testing kit as long as the following criteria are met:
 - Symptom duration <48 hours
 - Cough present or 2 or more respiratory symptoms present
 - i. Qualification for receipt of study drug will be determined based on a review of medical information with the tele-health provider. If the individual meets the required criteria (symptom duration <48 hours) and is diagnosed with probable influenza by a healthcare provider, this will trigger subsequent delivery of the intervention, if deemed appropriate.
2. Next, the ill individual will collect a nasal swab sample via self-swab or parent/legal guardian-swab as soon as possible. These specimens will then be packaged and shipping back to the laboratory via a delivery service for testing and further characterization. Additionally, the ill individual will complete day 0 of illness questionnaire in REDCap, which will ask information about respiratory and systemic symptoms, recent travel history, and absenteeism.
3. Concurrently, the participant will connect with a provider via the tele-health app previously downloaded on their smartphone. The provider will review the participant's symptoms and determine whether influenza infection is likely to be the underlying cause of the symptoms. If probable influenza is diagnosed, the tele-health provider will prescribe a weight-based dose of BXM. If antiviral treatment is not deemed appropriate by the tele-health provider, this information will be documented in the post-visit Care Plan for the study participant and subsequently shared with the study team.
4. Next, the study pharmacy will be notified that the participant is being prescribed BXM.

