All sick individuals, meaning those drug eligible and those drug ineligible, will complete an illness questionnaire in REDCap 7 days after they report the illness. This questionnaire will collect information on the presence or absence of respiratory and systemic symptoms during the 7 days after reporting the illness. Data will also be collected on childcare, school, and work absenteeism, and subsequent visits to health care providers. Additionally, the influenza-diagnosed individual will provide nasal swab specimens collected via self-swab or parent/legal guardian-swab at Study day 2-3 and Study day 5-7. These swabs will be returned to the laboratory via a delivery services the day of or the day after collection (See VI. Laboratory Procedures section). In addition to the illness questionnaire, the drug eligible, influenza infected participant will complete a standard questionnaire at 7 and 14 days following study drug receipt to monitor for the occurrence of adverse events (AEs) or serious adverse events (SAEs). These questionnaires will be monitored by a member of the study team. Additionally, any provider consultations with tele-health following drug administration will be reported to the study team to monitor for the occurrence of adverse events (AEs) or (SAEs). Any reported adverse events will be assessed to determine if related to drug treatment and whether unexpected or not and subsequently reported to the IRB using a standardized AE and SAE form. After the self-collected nasal swabs have been tested in the laboratory, the case will have to ability to view the results of their swab on the Seattle Flu Study website.

For all individuals that provide nasal swab specimens for testing and further characterization, they will have the ability to view whether influenza or respiratory syncytial virus (RSV) was detected from their swab(s) on the Seattle Flu Study website (See VI. Laboratory Procedures).

Data collection

Data will be collected electronically in REDCap online via a computer or mobile device or through a text-message accessible app. The major data collection activities will occur at the following times (See Table 1).

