 - **If influenza is not diagnosed**, the sick participant will provide one nasal swab collected via self-swab or parent/permanent legal guardian-swab, which will be mailed back to the laboratory. Additionally, the ill participant will complete an illness questionnaire at Study day 0, then again at Study day 7. The household will remain enrolled and continue to monitor for the development of a cough or 2 or more respiratory symptoms via the weekly symptom monitoring log.
 - **If influenza is diagnosed**, ill participant will provide a nasal swab sample collected via self-swab or parent/legal guardian-swab. Also, following a positive test result, the ill participant will complete Study day 0 of the illness questionnaire. This questionnaire will collect information regarding the presence, duration, and severity of respiratory and systemic symptoms in the ill participant. Additional information such as recent travel history, childcare, school, or work absenteeism as well as data on subsequent medical care will be collected on the questionnaire. Additionally, the 98point6 provider will confirm antiviral treatment is appropriate, and write a BXM prescription. Next, BXM will be delivered home of the case within 6 hours via a rapid delivery service.
- **Following delivery and therapy initiation**, the case will document the time of consumption.
- **At Study day 2-3 and Study day 5-7 after a positive test result**, the drug eligible, influenza-infected participant will provide nasal swab samples collected via self-swab or parent/legal guardian-swab. All nasal swabs will be mailed back to the laboratory for further testing the same day or the day following collection (see VI. Laboratory Procedures section). Also, the ill participant will complete an illness questionnaire 7 days after antiviral treatment. This questionnaire will collect information regarding the presence, duration, and severity of respiratory and systemic symptoms. Additional information such as recent travel history, childcare, school, or work absenteeism as well as data on subsequent medical care will be collected through the questionnaire.
- **Within 48 hours after drug receipt**, individuals will be screened for evidence of reaction to the drug using a standardized questionnaire in REDCap.

- **7 days and 14 days after drug receipt**, individuals will be screened for evidence of reaction to the drug using a standardized questionnaire.

Table 1. Timing of Data Collection

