Data Items	Enrollment	Weekly during Influenza Season	Monthly during Influenza Season	Influenza not diagnosed, drug eligible group	Influenza diagnosed, drug eligible group	Sick, drug ineligible group
Informed consent	X					
Baseline health and demographic data collected	X					
Baseline nasal swab collection	X					
Self-monitor cough or 2 or more respiratory symptoms		X				
Report changes in household structure or influenza vaccine status			X			
Nasal swab collection (Study day 0)				X	X	X
Nasal swab collection (Study day 2-3)					X	
Nasal swab collection (Study day 5-7)					X	
Illness questionnaire (Study day 0, Study day 7)				X	X	X

Record timing of drug receipt					X	
Standard questionnaire for AEs and SEAs (48 hours , 7 & 14 days post-treatment)					X	

Medication management

Baloxavir (BXM)

Drug eligible, influenza-infected study participants will receive a one-time oral dose of baloxavir (Xofluza) based on weight. For individuals weighing 80kg or more, they will receive 80mg of BXM. For individuals weighing 40-80kg, they will receive 40mg of BXM (See Table 2). The drug will be delivered to the individual's home within 2-6 hours of an influenza diagnosis. The case will be instructed to take the medication immediately on receipt and record the time of ingestion using the REDCap app or by text message. The description of the antiviral from the product monograph is as follows:

XOFLUZA™ is a polymerase acidic (PA) endonuclease inhibitor indicated for the treatment of acute uncomplicated influenza in patients 12 years of age and older who have been symptomatic for no more than 48 hours.

Limitations of Use: Influenza viruses change over time, and factors such as the virus type or subtype, emergence of resistance, or changes in viral virulence could diminish the clinical benefit of antiviral drugs. Consider available information on drug susceptibility patterns for circulating influenza virus strains when deciding whether to use XOFLUZA.

Medication storage and packing

BXM blister packs will be provided to the study team prior to the start of the influenza season by the drug manufacturer or purchased from the manufacturer. According to the manufacturer, baloxavir should be stored in its blister package at 20°C to 25°C (68°F to 77°F); excursions permitted to 15°C to 30°C (59°F to 86°F). Additional storage recommendations are provided below.

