For the secondary endpoints of symptom duration and severity, drug eligible and drug ineligible participants will be analyzed separately. Symptom severity will be measured on a 4-point scale (0 = no symptoms, 1 = mild, 2 = moderate, 3 = severe) for each influenza-associated symptom the participant reports experiencing. Influenza-associated symptoms the participant does not report as experiencing will be coded as 0. An additional analysis will be conducted comparing secondary endpoints for drug eligible, influenza-infected study participants that received and initiated treatment within 48 hours of symptom onset and those that initiated treatment later than 48 hours. Kaplan-Meier curves will be used to present and analyze time to resolution of symptoms, defined as the time when the influenza-positive participant reports experiencing no respiratory or systemic symptoms. For study participants who received BXM, a Cox proportional hazards model will be used to calculate the hazard ratio, 95% confidence interval, and p-value for symptom duration by group (therapy within 48 hours of symptom onset, and therapy after 48 hours of symptom onset). The analysis of drug ineligible study participants will use a similar approach but will cluster by household and use a robust variance for computing confidence intervals and p-values. For BXM recipients, symptom severity will be compared between groups (therapy within 48 hours of symptom onset, and therapy after 48 hours of symptom onset) using proportions for categorical measures of severity and Pearson's chi-square test, as well as using ordinal regression. As above, the analysis using ordinal regression of drug ineligible study participants will cluster by household and use a robust variance for computing confidence intervals and p-values.

For the secondary endpoints of maximum viral titer and duration of viral RNA detection, we will use t-tests or nonparametric alternatives and linear regression to assess maximum viral titer and Kaplan-Meier curves and Cox proportional hazards models to assess duration of viral RNA detection.

Interim Analysis

This study is being conducted over the course of one influenza season. Therefore, an interim analysis will not be performed.

Antiviral resistance analysis

The secondary outcome data regarding emergence of BXM resistance will be reviewed at the end of the influenza season via genome sequencing of the viral RNA.

Health economic analysis

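### Symptom resolution requires zero symptoms, but illness questionnaires stop at a Day 7 form with inconsistent anchors, and no time origin, censoring rule or later source of resolution dates is specified

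*Protocol*

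**What the plan says.** **Event.** Protocol XI (Statistical Analyses) takes resolution as the event, "defined as the time when the influenza-positive participant reports experiencing no respiratory or systemic symptoms". It plans Kaplan-Meier curves and, among baloxavir recipients, a Cox model comparing treatment within and after 48 hours of onset. Symptom duration is a listed secondary endpoint (Protocol III).

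**Schedule.** Protocol IV says that "all drug eligible and drug ineligible participants will receive a 7-day follow-up from the study team per illness episode". The Table 1 row reads "Illness questionnaire (Study day 0, Study day 7" and has no later visit.

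**Dating of the Day 7 form (Protocol V).**
- Follow-up: all sick participants "will complete an illness questionnaire in REDCap 7 days after they report the illness", and symptoms are asked for the same window: "This questionnaire will collect information on the presence or absence of respiratory and systemic symptoms during the 7 days after reporting the illness".
- Data collection, for treated cases: "the ill participant will complete an illness questionnaire 7 days after antiviral treatment".
- Onset of Symptoms, for drug-ineligible participants: the form is completed one week after day 0, but its recall window is described as covering symptoms, travel and "absenteeism in 7 calendar days following the onset of a cough in the ill participant".

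**Later contacts.** The weekly log runs to May 1 and asks about cough, or at least two respiratory symptoms. The day-14 questionnaire goes to drug recipients and monitors adverse events. SAP B3 plans a descriptive Table 1b from a weekly diary, including days sick, recovery status and severity for each symptomatic day.

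**SAP.** Symptom duration is objective S3, but section B6 gives no analysis for it.

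**The concern.** Under a zero-symptom definition, one lingering symptom at the last illness form means no event. The later contacts are not built to supply it. A participant with a single non-cough respiratory symptom, or with systemic symptoms only, looks well on the protocol's weekly log. The day-14 form is not described as asking when the last symptom ended.

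For the same treated participant, two sections of the protocol date the Day 7 form differently. The cough-onset window is undefined for someone who qualifies on two respiratory symptoms without cough. On the treatment clock, the last observation moves later with treatment delay, and delay is what the Cox model compares.

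At stake are the number of resolution events in a study expecting about 63 influenza cases, and the meaning of any figure for the proportion resolved by Day 7.

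**Working it through.** The documents give no expected duration, event count, power or censoring rate for this endpoint, so there is no planned figure to reproduce. The case count does reproduce: 0.25 × 250 = 62.5, stated as 63 (Protocol XI).

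**1. Last illness form, in days from onset.** Protocol V requires symptoms of less than 48 hours for self-testing and for drug qualification.
- Window from cough onset: 7.
- Dated from a report made 0 to 2 days after onset: 7 to 9.
- Dated from treatment within 48 hours: 7 to 9.
- Dated from treatment after 48 hours: more than 9.

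**2. Share censored (assumed durations).** For log-normal duration from onset with median *m* and log-SD *s*, the share unresolved at day *t* is P(T > t) = 1 − Φ(ln(t/m)/s). Example: m = 10, s = 0.4, t = 7 gives ln(0.7)/0.4 = −0.89, and 1 − Φ(−0.89) = 81%. Ranges below are over s = 0.4 to 0.6.

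| Median (days) | Day 7 | Day 9 | Day 14 |
|---|---|---|---|
| 4 | 8–18% | 2–9% | under 1–2% |
| 5 | 20–29% | 7–16% | under 1–4% |
| 7 | 50% | 26–34% | 4–12% |
| 10 | 72–81% | 57–60% | 20–29% |

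Of 63 cases, that is about 5 to 51 censored at day 7 and 1 to 38 at day 9. Exponential durations with the same medians give 30–62% and 21–54%.

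**3. Distortion of a resolved-by-Day-7 summary.** Give everyone the same true duration (assumed median 7 days, log-SD 0.5). The share seen to resolve by the form is then:
- 50% if the form falls 7 days from onset;
- 60% if dated from a report spread evenly over 0 to 2 days;
- 61% if dated from treatment at 0.25 to 2 days;
- 76% if dated from treatment at 2 to 4 days.

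The 2-to-4-day range is an assumption. On the planned timeline, a participant qualifying just under 48 hours who takes the drug on delivery 6 hours later is treated by 54 hours, or 2.25 days. Treatment at 2 to 2.25 days puts the form at 9 to 9.25 days. Φ(ln(9/7)/0.5) = 69% and Φ(ln(9.25/7)/0.5) = 71%. The late group therefore appears to resolve more often by about 8 to 15 percentage points, from the schedule alone.

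**4. Lost events (illustration).** With d events, late share p and hazard ratio HR, Schoenfeld power at two-sided 0.05 is Φ(√(d·p(1−p))·ln HR − 1.96). For 63 treated cases, p = 0.2 and HR = 2:
- no censoring: Φ(√10.08 × 0.693 − 1.96) = 60%;
- 25% censored: 48%;
- 50% censored: 34%.

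The late share and the hazard ratio are assumptions, and 63 is an upper figure because not every case will be treated.

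**The case against.** **Kaplan-Meier and Cox methods handle unequal censoring.** This stands. If time runs from onset and censoring is non-informative, different cut-offs do not bias the estimate. But the plan does not say that time runs from onset. If it ran from treatment, two people who both resolve on day 8, treated on days 1 and 2.25, would be given durations of 7 and 5.75 days.

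**The anchors are close in practice.** This largely stands. Delivery is planned within 2 to 6 hours of diagnosis, so report and treatment should usually fall near each other. The drug-ineligible form is completed one week after day 0, which is compatible with the report anchor, and its cough-onset phrase is a recall window that may attach only to absenteeism. The clear conflict is between report and treatment for treated participants.

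**Other data exist.** This stands in part. The data collection section says that the form for treated cases records symptom duration as well as presence and severity. The SAP diary includes recovery status and daily severity. The forms are not in the documents, so end dates cannot be assumed absent. Yet the diary items are assigned to a descriptive table and not linked to resolution.

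**Stronger readings.** A reader might infer that most of the endpoint is lost, or that the Kaplan-Meier median will not be reached. The documents give no duration from which to conclude either; at a 9-day cut-off, even a median somewhat above 7 days can be reached. A reader might also infer that treated and untreated durations are being compared unfairly. Protocol XI analyses drug-eligible and drug-ineligible participants separately, and the planned Cox contrast is among recipients.

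**Conclusion.** The point holds as a gap in endpoint ascertainment and specification. The illness questionnaire stops at a Day 7 form whose date conflicts between sections for treated participants. Those still symptomatic are right-censored at roughly 7 to 9 days from onset, later for late treatment on the treatment clock. No time origin, censoring rule or later source of resolution dates is specified.

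The size is uncertain: about 8 to 81% censored at 7 days and 2 to 60% at 9 days, resting wholly on the assumed log-normal durations. The share reaches half at a 7-day cut-off only if the median is about 7 days or more. It would be too strong to say that all follow-up ends at Day 7, since weekly logs continue, or that the survival analysis is necessarily biased. The supported harm is lost events and distortion of any resolved-by-Day-7 summary. This concerns a secondary endpoint of a feasibility pilot and leaves the primary outcome untouched. It is still worth correcting, because end dates that are not collected cannot be fully recovered afterwards.

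**What to change.** 1. Reconcile the three parts of Protocol V (Onset of Symptoms, Follow-up, Data collection) so that the Day 7 form and its recall window are dated from illness report for every ill participant.
2. State in Protocol XI and the SAP that time runs from symptom onset, and that those unresolved are censored at their last contact with symptom information, up to a common horizon.
3. Add two items per ill person to the Day 7 form: whether all symptoms have gone, and the calendar date the last one ended.
4. For those unresolved, repeat both items at a day-14 contact on the same clock for all groups: the existing day-14 form for drug recipients, and the weekly log covering day 14 for others. The recipients' form is dated from drug receipt, so its items must refer to day 14 from illness report. The log is a household form, so its items must be asked for each ill person.
5. Say whether the diary items in SAP B3 feed the endpoint.

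Under the assumed durations, observation to day 14 from onset lowers the unresolved share to at most 20 to 29%, even with a 10-day median. The cost is two items on forms already sent, protocol and SAP wording, slightly longer forms and some recall error in the end date. Clinical care is unchanged.

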Operations Committee: The Operations Committee will have primary responsibility for the implementation of the study protocol under the direction of the Executive Committee. They will develop and test all necessary study forms and procedures and produce a Manual of Operations that will document all procedures and methodology for the project. This committee will make recommendations to the Executive Committee regarding any proposed additions or alterations to the study protocol. The Operations Committee will meet on a regular basis, the schedule will be determined by the requirements of the study.

Data and Safety Monitoring Board: The purpose of the Data and Safety Monitoring Board (DSMB) is to provide external, objective advice to the Executive Committee regarding the safety and efficacy of the intervention being evaluated. This committee will be responsible for reviewing the data from the study on a regular basis, summarizing their conclusions and advice in a written set of minutes, and communicating this information to the Executive Committee. The PI will then forward these minutes to the Institutional Review Board at the University of Washington. The DSMB has specific responsibility to determine if there are problems relating to the safety of the intervention, to the degree the study should be stopped, and to determine if the study should be stopped early because the benefit of the interventions has proved to be stronger than originally anticipated. The Data and Safety Monitoring Board will meet just prior to the pre-season enrollment of households to review the final protocol, and after the conclusion of the influenza season. Voting membership on the Data and Safety Monitoring Board is limited to persons external to the investigative team. Senior members of the investigative team will serve as ex-officio members without voting rights. In addition to the voting members of the DSMB, study investigators will act as resources to the DSMB in a non-voting capacity.

Plan for reporting unanticipated problems/adverse events:

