Question: Does influenza incidence change when we look at varying testing timepoints (e.g. testing within 24, 48, and 72 hours of symptom onset)?

Details:

A sensitivity analysis will be performed to assess the effect of delayed testing on the intervention effect. The model will be re-run with three subsets of the data: those that were treated within 24, 48, and 72 hours of symptom onset. This will then be further analyzed with a time*age interaction. For example, we might expect that a 13-year-old might have more detectable RNA virus than an older adult at the same time point.

Data cleaning and software

All analyses will be performed in R version 3.6.1 using packages `'lme4'` and `'swCRTdesign'`.

C. Interim Analysis Plan

Original Plan

The DSMB will meet every month to review study progress and other issues as outlined below. In the proposed 6 month study, it is expected that the DSMB will meet X times.

Study progress and validity

At each monthly visit the DSMB will review data on enrollment, adherence of both households and household members, and all protocol violations. The DSMB will also compare the (pooled) observed influenza incidence rate to the (pooled) expected influenza rate to determine if the influenza incidence rate among study participants is at least as great as the incidence rate assumed in the study design, since incidence varies by influenza season. The DSMB will recommend any changes to the study design they believe are needed to ensure study validity.

Expected event rate: 150/1000 pdy in the control period and 120/1000 pdy in the intervention period; 135/1000 pdy overall.

Efficacy monitoring

Baloxavir-resistant influenza strain transmission

Additional testing and sequencing of non-influenza respiratory pathogens will also occur. Baloxavir resistance will be analyzed via interim analyses and monitored for the duration of the study. In the unlikely event that the incidence of the transmission of baloxavir-resistant strains of flu exceeds 20% of study participants, the study will be halted.

Tables and Figures

Table 1a. Sociodemographic characteristics of individual participants, SFS Household Intervention Study, 2019-2020 influenza season

Variable	Full sample n=	Cases only n=
Sociodemographic variables		
Age - median (range)		
Sex		
Male		
Female		
Race		
American Indian or Alaska Native		
Native Hawaiian or other Pacific Islander		
Black or African American		
White		
Multiple Races		
Other		
Prefer not to say		

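### The Protocol asks the DSMB to judge stopping but names no meeting during the season; the SAP plans monthly meetings and a 20% resistance halt that cannot be reached as worded; neither document says which governs

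*Protocol*

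**What the plan says.** **Protocol, section IX (Data and Safety Monitoring Board).** The board has "specific responsibility to determine if there are problems relating to the safety of the intervention, to the degree the study should be stopped", and must also judge whether to stop early for benefit. It is charged with "reviewing the data from the study on a regular basis", with no interval given. The only meetings named are that it "will meet just prior to the pre-season enrollment of households to review the final protocol, and after the conclusion of the influenza season".

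**Protocol, section XI.** Under Interim Analysis, the reason given is that the study lasts one season: "Therefore, an interim analysis will not be performed". Under Antiviral resistance analysis, the data on "emergence of BXM resistance will be reviewed at the end of the influenza season". The Translational analysis paragraph says resistance will be monitored but gives no timing.

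**SAP, section C.** "The DSMB will meet every month to review study progress and other issues as outlined below". The number of meetings is a blank: "it is expected that the DSMB will meet X times". The standing agenda is: "At each monthly visit the DSMB will review data on enrollment, adherence of both households and household members, and all protocol violations", plus a comparison of observed with expected pooled influenza incidence. Resistance is to be examined in interim analyses throughout the study, and the study stops if transmission of baloxavir-resistant strains passes 20% of study participants.

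**SAP, section B.** Its analyses are to be run at DSMB meetings as well as at the end. B3 metrics are updated monthly for the board. B4 covers serious adverse events and resistance.

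**Dates.** The SAP was last revised on 8 October 2019 and Protocol 3.1 is dated 14 January 2020. Neither says that it supersedes the other on monitoring.

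**The concern.** A board can act on its stopping duty only if it sees accumulating data while there is still something to stop. Of the Protocol's two named meetings, the first comes before enrolment, when there are no data, and the second comes after the season, when no dispensing remains. The phrase about regular data review points towards in-season looks but schedules none.

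The SAP describes a different arrangement: monthly meetings, in-season resistance analysis and a numerical halt. Staff, the board and the IRB could each follow a different document and each be compliant. At stake are whether an external body takes a cumulative look at safety during dosing, and whether the resistance halt is in force and could ever be triggered.

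**Working it through.** **1. The texts side by side**

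| Item | Protocol IX and XI | SAP B and C |
|---|---|---|
| Named DSMB meetings between 1 Nov 2019 and 1 May 2020 | 0 | monthly; number left as X (6 if monthly over the 6-month study) |
| Interim analysis | none | yes, for resistance |
| Timing of resistance review | end of season | throughout the study |
| Numerical halt | none | resistant-strain transmission above 20% of participants |
| Which document governs | not stated | not stated |

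The first three rows conflict directly. The fourth is a rule found only in the SAP.

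**2. Can the 20% halt be reached?**

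Inputs, from the attack-rate table in Protocol II (repeated in SAP B6): 250 households, household attack rate a = 25% (the highest row), secondary attack rate s = 18% to 38%, and mean household size h = 3, 4 or 5 including the case. Assumption: every household member enrols, so participants = 250 × h.

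Reproducing the plan's table:

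- Primary cases: 250 × 0.25 = 62.5, shown as 63.
- Secondary cases, 63 × (h − 1) × s: 22.7 to 47.9 (h = 3), 34.0 to 71.8 (h = 4), 45.4 to 95.8 (h = 5). These match the printed 23-48, 34-72 and 45-96.

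Threshold against the largest expected number of influenza cases of any kind:

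| h | Participants | 20% of participants | Maximum cases (primary + secondary) | Share of participants |
|---|---|---|---|---|
| 3 | 750 | 150 | 63 + 48 = 111 | 14.8% |
| 4 | 1,000 | 200 | 63 + 72 = 135 | 13.5% |
| 5 | 1,250 | 250 | 63 + 96 = 159 | 12.7% |

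Even if every expected influenza case were resistant, the count would stay below the threshold. Enrolling more households does not help: the share is a × [1 + (h − 1)s] / h, in which the number of households cancels, so the SAP's upper figure of 1,000 households gives the same answer.

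The household attack rate at which all influenza cases together would equal 20% of participants, with s = 0.38, is a = 0.20h / [1 + 0.38(h − 1)]:

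- h = 3: 0.60 / 1.76 = 34%
- h = 4: 0.80 / 2.14 = 37%
- h = 5: 1.00 / 2.52 = 40%

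All three exceed the plan's highest assumption of 25%, and each still requires every case to be resistant.

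**The case against.** The strongest case against is that safety is already watched during the season. Treated participants are screened at 48 hours, 7 days and 14 days. Under the adverse event reporting plan in Protocol IX, events that the investigators rate moderate or severe go at once to the safety officer (DSMB) and the IRB, and minor events reach the DSMB as a summary. Protocol V (Follow-up) sends assessed events to the IRB. The drug is a single licensed dose within its indication, with one recipient per household. All of this stands, and it limits the severity. A reader might infer that nobody oversees safety in season; the documents do not support that. What these routes lack is a scheduled cumulative look by the external board: they are mainly single-event reports, and the minor-event summary is undated.

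A reader might also infer that the Protocol leaves the 20% rule without any review behind it. That takes the rule from one document and the timing from the other. The rule is only in the SAP, which supplies its own interim analyses.

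Nor does the Protocol's statement on interim analysis bar a descriptive safety listing. It sits in the statistical section and rests on the one-season duration. Only the resistance timing truly conflicts.

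One could argue that the later Protocol prevails, or that the SAP subheading Original Plan marks section C as superseded. No text says so, and no replacement plan follows that subheading. If the Protocol did prevail, the monthly board review would disappear.

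Finally, the SAP may have meant another denominator, since B4 analyses resistance per influenza-positive test. That is plausible, but section C says study participants.

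**Conclusion.** The point holds as a conflict between documents with a limited safety consequence; it should be fixed. Under the Protocol's named schedule the board first sees study data when nothing is left to stop. Under the SAP it meets monthly. No text settles which applies. Unscheduled or additional DSMB meetings are not excluded by the Protocol, so the claim is about what is scheduled, not about what is forbidden.

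The resistance halt needs attention whichever document governs. Under the plan's own highest assumptions, influenza cases of any kind come to 12.7% to 14.8% of participants, below the 20% threshold. This rests on full enrolment of household members and on the attack rates in the Protocol II table. It means the rule is unreachable under the planning assumptions, not that it is impossible in every season.

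The early-benefit part of the board's duty adds little weight: this is a feasibility pilot without a control arm, and extra meetings would not make that judgement workable.

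**What to change.** 1. **One schedule in both documents.** Either adopt the SAP's monthly plan and fill in X, or name at least one in-season meeting of the existing DSMB plus an unscheduled review after a study-related serious adverse event. State which document governs if they differ.
2. **A cumulative safety listing on the agenda.** Include all adverse and serious adverse events to date, with the minor-event summary that Protocol IX already promises the board. Record a recommendation to the Executive Committee on whether dispensing continues.
3. **Settle the resistance halt.** Either delete it, or restate it with a reachable denominator, for example sequenced influenza-positive baloxavir recipients or their influenza-positive household contacts, and give an in-season review time. If it is kept, amend the resistance timing in Protocol XI to match. A restated rule should also set a minimum number sequenced. With an assumed true resistance of 10%, the chance of exceeding 20% is 7.0% with 10 sequenced (3 or more resistant) and 0.9% with 63 (13 or more).

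The cost is wording in Protocol IX and XI and SAP C, and one to about six short meetings. Dispensing might pause briefly while an event is reviewed. In-season sequencing is needed only if the halt is kept, and the SAP already plans it. No new committee and no extra participants are required.
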